6.2 Exclusion Criteria

Patients will be excluded for the following reasons:

- 1. Received a dose of a steroid medication in the past 7 days
- 2. Known allergy to dexamethasone
- 3. Immunosuppressed

- 4. Cushing's syndrome
- 5. Known diabetes mellitus
- 6. Known peptic or duodenal ulcer or other major gastrointestinal illness (ex. ulcerative colitis)
- 7. Known myasthenia gravis
- 8. Glaucoma
- 9. Febrile at triage
- 10. History of head trauma in the past 7 days
- 11. Presence of any known active infection (eg. on antibiotics or antivirals, diagnosed with active infection in the ED, etc)
- 12. Current secondary headache (as per the treating physician's clinical impression)

7. Study Design

[figure not shown]

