9.1 Study Medication Description

The study intervention will consist of an oral compound of dexamethasone, given orally at a one time dose of 0.6mg/kg to a maximum of 15mg. The dexamethasone will be compounded at the CHEO research pharmacy using a combination of dexamethasone sodium phosphate USP injection 10mg/mL (PRDexamethasone Omega Unidose; see product monograph) manufactured by Omega Laboratories Ltd. and Ora-Blend®, a flavored oral suspending vehicle manufactured by Galenova Inc. The compound is created by combining 10mL of the dexamethasone 10mg/mL sodium phosphate USP and 90mL of Ora-Blend®. The final oral suspension has a concentration of 1mg/mL of dexamethasone and a pinkish hue with a milky consistency. The appropriate dose for the participant will be drawn up into an oral syringe, which will be labeled for investigational use. The commercial label will not be present given that this study is blinded.

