9.2 Placebo Description

The placebo will comprise Ora-Blend®, a flavored oral suspending vehicle manufactured by Galenova Inc. Participants randomized to the placebo group will be given Ora-Blend® 0.6mL/kg for a maximum of 15mL. Ora-Blend® has a pinkish hue and a milky consistency. The appropriate volume for the participant will be drawn up into an oral syringe, which will be labeled for investigational use. The commercial label will not be present given that this study is blinded.

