11.1 Safety Assessments

As is described above, few adverse events are anticipated with single use of oral dexamethasone. The following are potential adverse events that could occur from single use of dexamethasone, as has been reported in the adult migraine literature as well as the pediatric literature where oral dexamethasone was used as a one time dose for other indications:

- Abdominal pain: In one pediatric study on single use oral dexamethasone in the pediatric population, 3.5% of patients reported abdominal pain. Should a patient experience significant abdominal pain after the administration of dexamethasone, the treating physician will administer analgesics at his or her discretion.
- Anaphylaxis/hypersensitivity reaction: Hypersensitivity reactions and anaphylaxis are listed as possible adverse drug reactions in the product monograph. In one of the adult intravenous dexamethasone studies, acute medication reactions occurred in less than 10% of the patients(24), and in one study a patient reported a rash(29). As per the product monograph, patients with anaphylaxis to dexamethasone will be managed in the ED with close monitoring of vital signs, airway support where required, appropriate doses of epinephrine and aminophylline if needed. Patients with hypersensitivity reactions will be closely monitored in the ED until the treating physician deems that discharge is safe. Treatment for hypersensitivity reactions will depend on the nature and severity of the reaction and will be administered at the discretion of the treating physician.
- Aseptic necrosis of the femoral and/or humeral head: Limited case reports have identified the possibility of aseptic necrosis of the femoral and/or humeral head following single doses of corticosteroids(46,47). Although this adverse event is exceedingly rare with single doses of corticosteroids, any patient reporting hip or shoulder pain in the ED will have anteroposterior and frog-leg radiographs of the hip(63) and/or shoulder radiographs to screen for aseptic necrosis of the affected joint. Should the radiographs not

reveal evidence of aseptic necrosis, an MRI will be pursued (63). Patients reporting the new onset of shoulder or hip pain during telephone follow-up will be instructed to return to the ED for an assessment. Patients with evidence of avascular necrosis will be urgently referred to Orthopedics for management.

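### Exclusion 2 covers known allergy to dexamethasone only, although every participant swallows the Ora-Blend vehicle

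*Combined protocol and SAP*

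**What the plan says.** Section 6.2 lists twelve exclusions. Item 2, "Known allergy to dexamethasone", is the only one about allergy. The list mentions no vehicle, excipient or component of the study product, and it has no general clause letting the investigator exclude a patient for another reason.

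Section 9.2 describes the comparator: "The placebo will comprise Ora-Blend®, a flavored oral suspending vehicle manufactured by Galenova Inc". Section 9.1 describes the active product: "The compound is created by combining 10mL of the dexamethasone 10mg/mL sodium phosphate USP and 90mL of Ora-Blend". It also gives the resulting strength: "The final oral suspension has a concentration of 1mg/mL of dexamethasone".

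Section 11.1 does consider allergic reactions among the possible adverse events: "Hypersensitivity reactions and anaphylaxis are listed as possible adverse drug reactions in the product monograph". The monograph in question is that of the dexamethasone injection.

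**The concern.** An allergy exclusion is meant to keep out patients with a documented reaction to something the trial will give them. Here the written rule covers the active drug, which only about half of the participants receive. It does not cover the flavoured vehicle, which all of them receive. For a child allocated to placebo, exclusion 2 gives no protection against the product actually swallowed.

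What is at stake is the safety of an occasional child whose allergy was already known and could have been screened out. The pilot is also intended to inform a larger multicentre trial (section 10.1). If the eligibility wording is carried forward, the same gap would apply to many more children.

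**Working it through.** **Inputs**
- Allergy exclusion: dexamethasone only (section 6.2, item 2).
- Active recipe: 10 mL of injection at 10 mg/mL plus 90 mL of Ora-Blend (section 9.1).
- Active dose: "given orally at a one time dose of 0.6mg/kg to a maximum of 15mg" (section 9.1).
- Placebo volume: 0.6 mL/kg, at most 15 mL (section 9.2).
- Participants: 20, allocated 1:1 (sections 7.2 and 7.4).

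**Step 1: reproduce the stated strength.** (10 mL × 10 mg/mL) / (10 mL + 90 mL) = 100 mg / 100 mL = 1 mg/mL. This matches section 9.1, so the recipe can be taken at face value.

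**Step 2: vehicle share.** 90 / 100 = 90% of the active suspension by volume. The placebo is all vehicle.

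**Step 3: vehicle volume per child.** At 1 mg/mL, 0.6 mg/kg is 0.6 mL/kg, and the cap is reached at 15 / 0.6 = 25 kg.

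| Weight | Volume given | Vehicle, placebo | Vehicle, active |
|---|---|---|---|
| 20 kg | 0.6 × 20 = 12 mL | 12 mL | 12 × 0.90 = 10.8 mL |
| 25 kg or more | 15 mL | 15 mL | 15 × 0.90 = 13.5 mL |

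These volumes show only that both arms receive the vehicle in substantial amount. They say nothing about how likely a reaction is. Section 4.1 gives the placebo volume per mg where section 9.2 gives it per kg. The two need reconciling, but the vehicle shares in step 2 do not depend on it.

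**Step 4: does another section supply the missing check?**
- *Section 7.3:* volunteers screen, and the treating physician confirms the migraine diagnosis and the absence of secondary headache. Allergy is not mentioned.
- *Section 7.5:* the volunteer may ask the physician about exclusion criteria, which leads back to the list in 6.2. The research assistant records past medical history, but no rule says what follows from a vehicle allergy found there.
- *Section 9.3:* the pharmacist consults the randomization scheme and prepares the product. No allergy check is described.
- *Section 11.6:* the investigator may discontinue a participant at significant risk. This applies to someone already in the study and is not an eligibility rule.

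None of these states a vehicle-allergy check.

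**Step 5: how often might it arise?** The documents give no frequency. Purely as an assumption, let p be the proportion of otherwise eligible children with a known vehicle allergy. The chance of at least one among 20 is 1 − (1 − p)^20.

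| Assumed p | Chance of at least one in 20 |
|---|---|
| 0.01% | 0.2% |
| 0.1% | 2.0% |
| 1% | 18.2% |

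Nothing in the documents supports any particular row. The top of the range should not be read as an estimate.

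**The case against.** The strongest reply is that this is a drafting matter with little consequence. The dose is single and is given by a nurse in an emergency department. A physician, a research assistant who takes a history and a pharmacist all come between screening and dosing. Ordinary allergy checks may well stop such a child from being dosed. The screening questionnaire (Appendix A) is not in the supplied text and may already ask about other allergies. The documents list no Ora-Blend ingredients and identify no excipients of the injection.

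Much of this stands. It shows that exposure of an allergic child is possible, not certain, and it keeps the point minor. It does not remove the gap: the routine checks are not written as a safeguard, and even a fuller questionnaire would not make vehicle allergy an exclusion while 6.2 is silent.

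A reader might also infer two stronger things that the documents do not support.

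- *That a vehicle common to both arms makes hypersensitivity hard to compare between them.* Section 10.2 only tabulates adverse events by group, so no such test is planned. A shared vehicle is also what a matched placebo is for. Excluding known allergy would not remove first reactions in either arm.
- *That section 11.1 deals with hypersensitivity only as a reaction to dexamethasone.* Its anaphylaxis sentence does name the drug, but the text on monitoring and treating hypersensitivity reactions is not tied to a cause. The adverse event definition in section 11.3 is broad enough to capture a vehicle reaction in either arm.

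**Conclusion.** The point holds as a gap in eligibility wording: exclusion 2 is narrower than the products given. It rests on a literal reading of sections 6.2, 9.1 and 9.2, and the dilution arithmetic agrees with the plan's own stated strength.

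The benefit of closing the gap is small, on the assumption that known vehicle allergy is rare and that routine care would catch some cases. The feasibility objectives, the sample size and the Fisher's exact comparisons are untouched. It would go too far to infer that an allergic child would certainly be dosed, or that the excipients of the injection are a demonstrated hazard. The case rests on Ora-Blend alone and on participant protection.

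**What to change.** Reword exclusion 2 to: *known allergy or hypersensitivity to dexamethasone or to any component of the study suspensions, including Ora-Blend*. Check the screening questionnaire in Appendix A and add the same question if it is not already there.

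The cost is one phrase in section 6.2 and, if needed, one item on the screening form. The loss of recruits should be negligible if the allergy is as rare as assumed. No change to the analysis is needed.

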7.1. Description

The proposed study will be a Phase III pilot trial, designed as a 2-arm, parallel-group, randomized, placebo-controlled, double-blind study.

7.2 Description of the Study Stages

Twenty children and adolescents will be enrolled into this trial. The expected duration of the study will vary from patient-to-patient based on how many interventions for acute migraine pain will be administered, and these decisions will be made at the discretion of the treating physician. On average, it is expected that the duration of study participation in the ED will vary between 2 and 6 hours. There will be either a telephone follow-up with a research assistant approximately 48 hours after discharge and then a second telephone follow-up 7 days after discharge, or an email follow-up at 48 hours and 7 days with electronic questionnaires sent directly to participants, depending on participant preference.

Figure 3. Study Flow Diagram

7.3 Screening

Patients presenting to the CHEO ED with a triage diagnosis of headache, migraine or a related term (eg. head pain) who are interested in discussing the study will be screened for eligibility by SUPPORT (Students Undertaking a Pediatric Program of Research Training) volunteers. The SUPPORT program is a specialized volunteer program at CHEO that trains volunteers to assist in recruiting patients to clinical studies based in the ED. Prior to approaching potentially eligible patients, the SUPPORT volunteer will ask the patient if they are willing to discuss the study with them. Should a patient agree, the SUPPORT

volunteer will introduce the patient and their family to the study and if they are interested, they will carry out the eligibility screening (see Appendix A for screening questionnaire). If a participant is deemed eligible from the screening questionnaire administered by the SUPPORT volunteer, the volunteer will first ask the treating physician to verbally confirm that they agree with the diagnosis of migraine and that secondary headache is not present, and if the physician agrees, the volunteer will then notify the research assistant about the potential participant.

The research assistant will then meet with the potential participant to initiate the consent process. For patients over the age of 16, verbal and written consent will be sought from patients and their parent or guardian by the study assistant. For patients under the age of 16, verbal and written assent will be sought from the patient, and verbal and written consent will be sought from the parent or guardian. Study packages including consent forms, informational brochures and pre-printed orders for enrolled participants will be stored in the ED. There will be three sets of packages, one for each stratum, and the packages will be prelabeled with a numeric randomization code from the randomization scheme which will also serve as the participant identification number.

The Maternal, Infant, Child and Youth Research Network (MICYRN) tool, an instance of Research Electronic Data Capture (REDCaP)(56), is a secure, webbased, encrypted application and will be used for screening potentially eligible participants and for all data entry for enrolled participants. Basic demographic characteristics of patients who were screened for enrollment and who were ultimately excluded will also be recorded in MICYRN by the SUPPORT volunteers, along with the reason for exclusion (eg. declined, ineligible, etc; see Appendix B). The demographic characteristics that will be recorded for excluded patients will be the following: sex, age, Canadian Triage and Acuity Scale (CTAS) score and time of presentation (time of day) (see Appendix B).

Table 2. Study Schedule

Procedure	Screening	Baseline	Randomization/ Treatment	2 hours	Discharge	48 hour follow up	7 day follow up
Recording of	Х		Treatment	Hours		lonow up	lonow up
reasons for refusal,							
missed enrollment,							
etc							
Assessment of	Х						
eligibility criteria							
Contact information		х					
Vital signs		х					
Demographics and migraine history		Х					
Physical exam		Х					
Urine pregnancy		Х					
test (where							
applicable)							
Pharmacy carries			X				
out randomization							
Dispense study			X				
intervention							
Assessment of pain		X		X	X	X	X
intensity							
Assessment of				X	X	X	X
patient satisfaction							
Assessment of						X	X
missed time at work							
or school							
Assessment of				X	X	X	X
adverse events							
Assessment of						X	X
headache							
recurrence							

7.4 Randomization

Patients consenting to participation and meeting eligibility criteria will be randomly assigned to receive either dexamethasone or placebo in a 1:1 ratio. Prior to randomization, the research assistants will ensure that the baseline assessment is complete (see case report form in Appendix C) and that contact information is collected for the purposes of follow-up (see paper-based contact information form in Appendix D). Randomization will be stratified according to the length of current migraine duration (less than 2 hours, ≥ 2 and < 24 hours or ≥ 24 hours). Within each stratum, randomization will be blocked in blocks of four. A statistician will create the randomization scheme. The statistician will generate a list of random numbers for each stratum that will correspond to

specific group assignments. Group assignment will be encoded using a digit numeric coding system rather than a dichotomous group A or B system to better ensure blinding. The list will be sent to the research pharmacy and will not be accessible to anyone involved with the study outside of the pharmacy. The allocation will remain concealed to all study participants, study personnel and clinical staff.

The research pharmacists will maintain a password-protected list of the patients' names, their assigned numeric codes, their hospital identification numbers and their group allocations. Only the research pharmacists will have access to the list linking the assigned numeric code and group allocation to the patient's name and identifying information. In addition, the data safety monitoring board, or, where necessary, clinical staff or study investigators, will be given access to specific pertinent data from the list if safety issues or adverse events occur.

7.5 Baseline Assessment

The baseline assessment will involve a physical exam, which will be carried out by the ED physician as part of routine clinical care. After eligibility screening, the SUPPORT volunteers will confirm with the physician that a physical exam was done and that secondary headache was ruled out on physical exam. At this time, should the SUPPORT volunteer have any concerns about exclusion criteria (eg. presence of active infection) that were not resolved after talking to the patient and family, they can also ask the ED physician about their opinion regarding exclusion criteria given data acquired from the physician's history and physical exam.

In addition to the physical exam, the research assistant will take a targeted migraine history, record the patient's past medical history, record the vital signs from the chart and identify the baseline pain level of the patient using a 4-point scale where 0=no headache, 1=mild headache, 2=moderate headache and 3=severe headache (see Appendix C). The headache history will include questions pertaining to migraine diagnosis, presence of aura, headache duration, headache frequency, headache intensity, baseline migraine-related disability as measured by the Pediatric Migraine Disability Assessment (PedMIDAS) questionnaire (see Appendices C and E), and treatment of the headache prior to presentation to the ED (see Appendix C). The four point pain rating scale is being used in accordance with the recommendation set out in the International Headache Society guidelines for controlled trials of drugs in migraine(11).

7.6 Study Intervention Administration and Efficacy Assessments

Once the baseline assessment is completed, the study intervention will be administered. Acute pain interventions will also be administered at the discretion of the treating physician. Pre-printed orders will be prepared by the research pharmacy in order to simplify study procedures and prevent errors. The pre-printed orders will be stored in study packages along with the consent forms and the informational brochures (see Appendix F). Three sets of study packages will be stored in the ED: one for each randomization stratum. The study intervention will be administered by the treating nurse.

A research assistant will assess pain 2 hours post-intervention and at the time of discharge, using the 4-point rating scale described above. Should the patient be discharged prior to the 2 hour post-intervention time point, the discharge pain assessment will replace the 2 hour post-intervention assessment. At the time of discharge, patient satisfaction will also be assessed by the research assistant, using a 5-point Likert scale where 5=very satisfied, 4=satisfied, 3=neutral, 2=unsatisfied, 1=very unsatisfied. In the event where a participant is discharged prior to having an efficacy assessment by the research assistant, an electronic questionnaire will be sent to the participant as a proxy for the inperson ED discharge assessment. If adverse events are reported on the electronic questionnaire, then the participant will be called to further assess the adverse event(s).

7.7. Follow-Up

In the ED, study participants will receive a brochure (see Appendix F) about the study from the research assistant at the time of enrollment. The brochure will briefly describe the aims of the study, and will detail the timing and options for follow-up.

Participants will be offered the option of completing their follow-up via a self-administered electronic questionnaire sent through MICYRN, or over the phone with a research assistant. If they chose the option of the self-administered electronic questionnaire, they will receive an email with a link to the MICYRN-based questionnaire at 48 hours and 7 days post-intervention. Should they not complete the given questionnaire within 24 hours of their first notification, a second email will be sent. Should they fail to complete the given questionnaire within 24 hours of the second notification, the research assistant will contact them over the telephone for the given follow-up.

For participants selecting the option of telephone follow-up, the research assistant will call the patient for a follow-up telephone-administered questionnaire approximately 48 hours after discharge and 7 days after discharge (see Appendix C). In the event where it is not possible to contact a patient for follow-up over the telephone after several attempts, follow-up

questionnaires will be emailed to the participant through MICYRN with 24 hours reminders as above.

When an adverse event is reported during follow-up on one of the electronic questionnaires, the participant will be contacted over the telephone in order to clarify details pertaining to the adverse event.

Participants who complete both follow-up questionnaires will be sent electronic gift cards for Chapters Indigo in the amount of 10\$ via email.

7.8. Chart Review

The research assistant will review the chart 7 days after admission or later in order to record any return visits to the ED. Return visits will be coded as either headache-related or unrelated (see CRF in Appendix C).

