Methodology	Randomized, double-blind, 2-arm parallel group trial				
Study Duration	6 months				
Study Center(s)	Single center: Children's Hospital of Eastern Ontario				
Objectives	To determine the feasibility of carrying out a multicenter randomized controlled trial to assess the efficacy of oral dexamethasone for preventing migraine recurrence in the pediatric ED through the implementation of a pilot randomized trial. The primary scientific objective will be to determine if oral dexamethasone is superior to placebo in preventing migraine recurrence within 48 hours of ED discharge amongst pediatric patients presenting to the ED with migraine.				
Number of Participants	20				
Diagnosis and Main Inclusion Criteria	Children and adolescents aged 8-18 years with migraine according to modified International Classification of Headache Disorders 3 rd edition (beta version) criteria				
Study Product, Dose, Route, Regimen	Dexamethasone 0.6mg/kg PO as a one time dose given in the emergency department (maximum of 15mg)				
Duration of administration	Single dose in the emergency department				
Reference therapy	Placebo				

Statistical Methodology Fisher's exact test will be used to compare the two groups on the primary outcome and on the secondary outcomes that involve proportions. Adverse events will be presented descriptively in tabular form, with the frequency and percentage of each adverse event listed by the corresponding group.		on the primary outcome and on the secondary outcomes that involve proportions. Adverse events will be presented descriptively in tabular form, with the frequency and percentage of each adverse event listed by the
---	--	--

4. Background Information and Clinical Data

Headache is very common in the pediatric population, with an estimated worldwide prevalence of 58.4% amongst children and adolescents(1). Given its prevalence, it is not surprising that it accounts for a significant proportion of pediatric emergency department (ED) visits: anywhere from 0.8-1.3% of all pediatric ED visits are due to headache(2–5). Although the majority of pediatric ED visits for headache are due to secondary causes, migraine accounts for between 5.4% and 28.7% of these visits(2–6).

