5.3 Secondary Research Questions

- 1. To determine if oral dexamethasone is superior to placebo in preventing migraine recurrence within 7 days of ED discharge amongst pediatric patients presenting to the ED with migraine.
- 2. To determine if oral dexamethasone is superior to placebo in preventing return ED visits within 7 days of ED discharge amongst pediatric patients presenting to the ED with migraine.
- 3. To determine if oral dexamethasone is superior to placebo in terms of the proportion of patients achieving persistent pain freedom 48 hours after ED discharge amongst pediatric patients presenting to the ED with migraine.
- 4. To determine if oral dexamethasone is associated with differential rates of patient satisfaction as compared to placebo amongst pediatric patients presenting to the ED with migraine.

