7.8.2 Secondary Outcomes

Several secondary outcomes are of interest:

- 1. Pain intensity will be assessed at baseline, 2 hours after having received the study intervention (or at the time of ED discharge if prior to 2 hours) and at the time of ED discharge. As is suggested in the International Headache Society guidelines for controlled trials of drugs in migraine(11), pain intensity will be measured using a 4-point scale where 0=no headache, 1=mild headache, 2=moderate headache and 3=severe headache.
- 2. Persistent pain freedom, defined as the proportion of patients in each group who achieved pain freedom at 2 hours (or at the time of ED discharge if prior to 2 hours) and were free of pain without the use of rescue medication at 48 hours(11), will be assessed.
- 3. Patient satisfaction will be assessed at discharge and again at follow-up with the following 5-point Likert scale: 5=very satisfied, 4=satisfied, 3=neutral, 2=unsatisfied, 1=very unsatisfied.
- 4. The proportion of patients in each group with recurrence within the 7 days following ED discharge will be assessed. The 7 day time point was selected based on its use in a previous study(29) and given our interest in exploring potential longer treatment effects of dexamethasone for this indication.
- 5. The number of patients with return ED visits within 7 days of ED discharge will be assessed through chart review.
- 6. Adverse events will also be queried at 2 hours (or at the time of ED discharge if prior to 2 hours), at discharge and in the follow-up questionnaires.

8. Expected Duration of Participant Participation

Participants will remain in the ED for variable lengths of time depending on the time required for the acute pain interventions to alleviate the migraine pain. It is anticipated that participants will remain in the ED for 1.5-6 hours on average. Participants will also be asked to complete two electronic or telephone follow-up questionnaires, which are expected to last a maximum of 5 minutes per follow-up. Participation in the study will end after the second follow-up electronic or telephone questionnaire, that is, 7 days following discharge.

9. Study Medication

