11.2 Methods and Timing of Safety Assessments and Follow-Up

As is described above, assessment of adverse events will occur during the ED visit at 2 hours post-intervention (or at the time of ED discharge if prior to 2 hours) and at discharge. During the 48 hour and 7 day electronic or telephone follow-ups, participants will again be asked if any adverse events have occurred. In the events where a participant indicates that an adverse event has occurred, they will be asked to describe those adverse events either in written form (for those completing electronic questionnaires) or verbally (for those completing telephone questionnaires). Participants completing electronic questionnaires and endorsing adverse events at follow-up will also be contacted over the telephone to clarify the nature of the adverse events. The Qualified Investigator or co-investigator will assess the potential relatedness of each AE to the investigational product during the trial.

All participants experiencing adverse events in the ED will be contacted over the telephone for follow-up (as opposed to being offered the option of electronic follow-up). Follow-up of adverse events occurring in the ED will also occur during the 48 hour and 7 day telephone follow-ups. In instances where the adverse event is first reported at the 7 day follow-up, an additional telephone follow-up 48 hours after the 7 day follow-up will be scheduled.

Although general follow-up timeframes are described above, extended follow-up will occur as required when the event does not resolve or stabilize within the above timeframes and the frequency, nature and timing of the extended follow-up will be determined by the Qualified Investigator. In addition, the Qualified Investigator may choose to schedule in-person follow-up in lieu of telephone follow-up when deemed necessary for participant safety.

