- a. for an "expected" serious ADR, an increase in the rate of occurrence which is judged clinically important;
- b. a significant hazard to the patient population, such as lack of efficacy with a drug used in treating a life-threatening disease; and
- c. a major safety finding from a newly completed animal study.

As per the ICH Good Clinical Practice Guidelines stipulations, the Children's Hospital of Eastern Ontario Research Ethics Boards will establish, document in writing and follow procedures for:

- Determining the frequency of continuing review as appropriate (including adverse drug reactions and adverse events) and
- Requiring that the **Investigator** should promptly report to the REB
 - Changes increasing the risk to subjects and/or affecting significantly the conduct of the trial;
 - All adverse drug reactions that are both serious and unexpected
 - New information may affect adversely, the safety of the subjects or the conduct of the trial.

In additions to the reporting to Health Canada as described above, all serious adverse events that occur at CHEO along with any adverse events that are both serious and unexpected, will be reported to the CHEO Research Ethics Board.

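### Return ED visits within 7 days are measured by chart review alone in a single-centre trial, so visits to other EDs would go uncounted

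*Combined protocol and SAP*

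**What the plan says.** Section 5.3, question 2, sets the aim: "To determine if oral dexamethasone is superior to placebo in preventing return ED visits within 7 days of ED discharge". It names no hospital.

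Section 7.8 gives the procedure: "The research assistant will review the chart 7 days after admission or later in order to record any return visits to the ED". Visits found are then coded as headache-related or not. Section 7.8.2, item 5, defines the outcome by the same source: "The number of patients with return ED visits within 7 days of ED discharge will be assessed through chart review". The synopsis describes the trial as "Single center: Children's Hospital of Eastern Ontario".

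The follow-up columns of Table 2 cover pain, satisfaction, missed work or school, adverse events and headache recurrence. They list no item on ED visits or admissions. Section 10.2 compares the proportions with return visits by Fisher's exact test and gives no rule for visits made elsewhere.

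Adverse events have a different source. Section 7.8.2, item 6, has them queried in the ED, including "at discharge and in the follow-up questionnaires". Section 11.2 says that at 48 hours and 7 days "participants will again be asked if any adverse events have occurred".

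**The concern.** The question and its measurement do not match. A family that goes to another ED during the week has made a return ED visit in the sense of question 2, yet leaves no trace in the source that defines the outcome. Nothing in the text says that other hospitals' records are sought, or that a participant's own report of a visit would count.

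The error runs in one direction: a missed visit can only lower the proportion. The background section treats return visits as a burden on the health system, and section 10.1 says that the pilot data are to inform a multicentre trial. An undercounted rate, and the definition that produced it, could both be carried into that design.

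**Working it through.** **Comparing the passages.** Question 2 in 5.3 has no hospital limit. Sections 7.8 and 7.8.2 item 5 name chart review and no other source. With a single centre, the chart is most naturally the study hospital's. Section 10.2 needs a yes or no for each participant, so someone with no visit in the chart would most naturally be entered as a no. The last two steps are inferences, since the text states neither whose chart it is nor how outside visits are coded.

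**Inputs for scale.** The plan has no figure of its own to reproduce here.
- N = 20, allocated 1:1, so about 10 per arm (7.4, 10.1).
- Background return rate p = 5.5% within 3 days (section 4). No 7-day rate is given. I take 5.5% as the rate of returns to any ED.
- Share of returns made to another hospital, m: not given. Assumed range 10% to 40%.

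**Formulas and results.**
- Expected participants returning: N × p = 20 × 0.055 = 1.1.
- Measured rate: p × (1 − m). At m = 10%, 5.5% × 0.90 = 5.0%. At m = 40%, 5.5% × 0.60 = 3.3%.
- Expected participants whose return is missed: N × p × m. At m = 10%, 1.1 × 0.10 = 0.11. At m = 40%, 1.1 × 0.40 = 0.44.
- Chance of missing at least one: 1 − (1 − p × m)^20. At m = 10%, 1 − 0.9945^20 = 10%. At m = 40%, 1 − 0.978^20 = 36%.

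**Effect on the test.** With 10 per arm and none returning in one arm, two-sided Fisher p is 0.087 for 0 v 4 and 0.033 for 0 v 5. Significance needs at least 0 v 5, against about one return expected in the whole trial. A missed visit would hardly change the test result.

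**Timing.** Section 7.8 counts 7 days from admission, while 7.8.2 item 5 counts 7 days from ED discharge. With expected ED stays of 2 to 6 hours (7.2) or 1.5 to 6 hours (section 8), a review at exactly 7 days from admission would close a few hours before the outcome window. The wording permits a later review but does not require one.

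**The case against.** The strongest reply is that little is at stake. Return visits are one secondary outcome and are not among the five pilot aims in 5.1, where the outcome proportion to be estimated is 48-hour recurrence. The share going elsewhere is assumed, it is applied to a 3-day rate for a 7-day outcome, and the expected number missed is below one. All of that stands, and it limits the point to a cheap improvement in ascertainment.

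It can also be said that the follow-up questionnaire is in Appendix C, which is not in the text available here and may already ask about visits elsewhere. Table 2 cannot settle this, because it is not exhaustive: it has no row for the chart review either. But even if the question is asked, 7.8.2 item 5 defines the outcome by chart review, so the answer would not count. A third reply is that in a single-centre protocol a return to the ED may simply mean that ED. In that case the label in 5.3 and 7.8.2 should say so.

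A reader might go further and infer that serious events treated elsewhere would be missed in the same way. The documents do not support that. Adverse events are asked about directly at both follow-ups. Events reported electronically lead to a telephone call, and those first reported at 7 days lead to another call 48 hours later (11.2). The hospital-stay criterion in 11.3 has no site limit, and 13.2 sends all serious adverse events to the DSMB. Section 11.4 does describe the events for the ethics board as "all serious adverse events that occur at CHEO along with any adverse events that are both serious and unexpected", but the second half of that phrase has no site limit, and in a single-centre trial the first half may simply mean this site's participants. At most, that is ambiguous wording.

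**Conclusion.** The point holds for the return-visit outcome. As written, a visit to another ED within 7 days would not be captured and would most naturally be analysed as no return, so the proportions are biased downward. On the assumed 10-40% share, a true 5.5% would be measured as 5.0-3.3%, with about a 10-36% chance of missing at least one participant's return among 20. The consequence is for the estimate carried forward; the 10 v 10 comparison is practically unaffected. The conclusion rests on reading the chart as the study hospital's and on the absence of a stated coding rule for outside visits. It does not extend to a gap in detecting serious adverse events. The mismatch between admission and discharge as the starting point is a matter of hours, worth correcting along with the rest.

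**What to change.** - Add one item to the existing 48-hour and 7-day questionnaires: any ED visit or hospital admission, at any hospital, since discharge, with date and reason. If Appendix C already has such an item, only the next change is needed for ascertainment.
- In 7.8.2 item 5, count a return visit if it is found by chart or by questionnaire, and show the two sources separately.
- In 7.8, time the chart review from ED discharge, no earlier than 7 full days after it, to match the outcome window.
- If the sponsor prefers chart review only, label the outcome in 5.3 and 7.8.2 as return visits to the study hospital.

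The cost is one questionnaire item in contacts that already take place, plus a few words in two sections. The small downside is that off-site visits would rest on self-report, which is why the two sources should be shown separately.
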